11 EFFICACY ANALYSES

Efficacy will be conducted on the ITT and FAS for US (FDA) submission. Efficacy analysis of non-inferiority on the PPS population and superiority on FAS population will be used for EU regulatory submission.

The **Efficacy Emergent Period** is defined as the evaluation period from the Analysis date of first dose intake up to 7 days after the Last Dose of study drug or EOT Visit, whichever occurs first. This period will be used as reference period for the time to event analyses related to efficacy endpoints, unless specified otherwise.

11.1 Analyses of Primary Endpoint

11.1.1 Primary Endpoint and Hypothesis

11.1.1.1 U.S. Submission

The primary efficacy endpoint for the US (FDA) submission is defined as the hemoglobin change from baseline to the average level during the evaluation period defined as Week 28 until Week 52.

The primary hypothesis to be tested for the primary efficacy analysis for US (FDA) submission is:

H_0 : Hemoglobin mean change from baseline to the average level from Week 28 to Week 52 in the roxadustat group \leq hemoglobin mean change from baseline in the epoetin alfa group minus 0.75 g/dL

Versus:

H_1 : Hemoglobin change from baseline to the average level of Week 28 to Week 52 in the roxadustat group $>$ hemoglobin mean change from baseline in the epoetin alfa group minus 0.75 g/dL

A Multiple Imputation (MI) analysis of covariance (ANCOVA) model will be used. The model will contain terms for treatment group, baseline Hb measurement, and stratification factors except mean qualifying screening hemoglobin (≤ 10.5 vs. >10.5 g/dL). The primary efficacy analysis will be based on the estimated difference between the two treatments overall mean effects throughout the evaluation period based on the pooled ANCOVA model.

This null hypothesis will be rejected if the two-sided 95% CI for the difference between the two treatment groups using MI ANCOVA model lies entirely above -0.75 g/dL. Hemoglobin values under the influence of a rescue therapy will not be censored in this analysis.

The below stratification factors will be used in efficacy analyses.

- Mean qualifying screening hemoglobin (≤ 10.5 vs. >10.5 g/dL) for other than Hb related endpoints
- History of CV, cerebrovascular, or thromboembolic diseases (yes vs. no)
- Mean prescribed weekly epoetin alfa dose (or, equivalent epoetin dose for nonepoetin subjects) in the 4 weeks prior to randomization (≤ 150 vs. > 150 IU/kg/week)
- Incident dialysis within ≤ 4 months vs. > 4 months of starting dialysis when randomized.

The following steps will be used to conduct the primary analysis of the primary endpoints for both regions:

1. Generate 200 datasets, using seed 162345 for U.S. and 347631 for Ex-U.S., where only intermittent missing hemoglobin data will be imputed for each treatment relying on non-missing data from all subjects within each treatment group using the Monte Carlo Markov Chain, MCMC) imputation model and the available non missing hemoglobin for each scheduled Week by treatment group.

The MCMC statement in the SAS PROC MI procedure with monotone option will be used. As a result, each dataset will only have missing ending data, namely, a monotone missing data pattern.

2. For each dataset from step 1, missing ending data (hemoglobin up through end of evaluation period) will be imputed. As a result, 200 imputed complete datasets will be generated.
 - Missing data at Week 1 will be imputed using the regression imputation model with baseline stratification factor, baseline and hemoglobin from Week 1, using the SAS PROC MI procedure with the REGRESSION option in the MONOTONE statement.
 - The SAS PROC MI procedure will use data separately from each treatment subjects to impute the missing data for a specific Week (i.e. only those that need the imputation for the Week). Since subjects from the different treatment groups for that Week are excluded from the step, they will not contribute to the imputation for the Week.
 - Repeat for all other scheduled Weeks sequentially (Week 2 to the end of evaluation period). Subjects whose missing data were imputed for previous Weeks will contribute to the imputation for the current Week.
 - The regression imputation model includes an intercept and the slopes of the hemoglobin from previous Weeks.
3. Analyze each imputed complete dataset using the ANCOVA model using the mean of observed or otherwise imputed Hb values within the evaluation period (week 28 -52). The model will contain terms for baseline Hb measurement as a covariate and treatment group and stratification factors except mean qualifying screening hemoglobin (≤ 10.5 vs. >10.5 g/dL) as fixed effects.

Sample SAS code:

```
PROC MIXED data=xx;
  class treatment categorical covariates;
  model change_Week36 = treatment covariates / solution;
  lsmeans treatment / diff cl;
  ods output Diff=lsdiffs LSM=lsm solutionF=Parms;
  by _Imputation_;
run;
```

4. Combine estimates from the results for each of the 200 ANCOVA model using SAS PROC MIANALYZE.

Sample SAS code:

```
PROC MIANALYZE parms(classvar=full)=lsdiffs;
  class treatment categorical covariates;
  modeleffects treatment;
  ods output ParameterEstimates=MIAN_ lsdiffs;
run;
```

Report the results of the least-squares mean estimates of the change from baseline in hemoglobin during the evaluation period, the estimates of treatment effect (e.g. least-squares mean CFB in hemoglobin for the treatment group minus the least-squares mean CFB in hemoglobin for the active comparator group) and the corresponding p-values during the evaluation period.

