	
 
• Mean qualifying screening hemoglobin (<math>\leq 10.5</math> vs. <math>>10.5</math> g/dL)
 
• History of CV, cerebrovascular, or thromboembolic diseases (yes vs. no)
 
• Mean prescribed weekly epoetin alfa dose (or, equivalent epoetin dose for non-epoetin subjects) in the 4 weeks prior to randomization (<math>\leq 150</math> vs. <math>> 150</math> IU/kg/week)
 
• Geographical region (US vs. Ex-US regions)
 
 
Sample size determination:
 
At least 600 subjects will be enrolled in this study. During the course of this study, which is being conducted in parallel with other Phase 3 studies, up to 1200 subjects may be enrolled for safety evaluation of roxadustat in comparison to epoetin alfa including adjudicated and prespecified safety events of interest (ie, all-cause death, MI, stroke, congestive heart failure requiring hospitalization, unstable angina requiring hospitalization, DVT, pulmonary embolism, vascular access thrombosis, and hypertensive emergency). The final number of patients to be enrolled will be based on the enrollment rate of other studies within the same indication, in order to optimize stopping these studies at comparable time frame
 
With at least 600 subjects, the study will provide at least 99% power to demonstrate statistical noninferiority of roxadustat versus ESA in the primary endpoint for US (FDA) submission (ie, specifically, Hb change from baseline to the average level during the evaluation period defined as Week 28 until Week 52).
 
The study will provide at least 99% power to demonstrate statistical noninferiority of roxadustat versus ESA in the primary endpoint outside of the United States (ie, specifically, Hb change from BL in the averaged Hb over Weeks 28 to 36).
 
This assumes a difference (roxadustat minus ESA) of <math>-0.30</math> g/dL, a noninferiority margin for this difference of <math>0.75</math> g/dL and a standard deviation of <math>1.25</math> g/dL.
 
Analysis Sets
 
For US regulatory submission, efficacy and safety analyses will be based on all subjects stratified by the protocol amendment, on subjects enrolled during the original protocol but before the amendment, and on subjects enrolled after the amendment separately.
 
For EU regulatory submission, efficacy and safety analyses will be based on subjects enrolled during the original protocol before the

--	---

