### **4.2 Randomization, Treatment Assignment, and Rationale for Open-label Design**

A randomized design has been chosen in order to ensure a balanced and unbiased allocation of study subjects to the treatment arms and to minimize bias in therapeutic management and in outcomes assessment.

An open-label design was chosen since double-blinding would require a double-blind, double-dummy design to match the different ESAs made by different manufacturers having different dosing specifications which is considered too challenging without much added benefits to the study. It would expose subjects to multiple additional injections or infusions without additional benefit. Furthermore, the difference in iron supplementation requirements between roxadustat and the ESA will further complicate any efforts to blind, or alternatively end up in inadvertent unblinding. The high probability of these confounding factors rendering the conduct of a double-blind double-dummy study and data becoming invalid is outweighing the advantage of a lower risk for bias. Therefore, in light of the objectivity of primary endpoint measures not influenced by blinding and the lack of operational feasibility without addition of values to subjects, the open label study design is to be considered the most reasonable option.

A total of up to approximately 1200 subjects are planned to be randomized in an open-label, 1:1 ratio to receive either of the following two treatments:

- Roxadustat (up to approximately 600 subjects)
- Active Control: epoetin alfa (up to approximately 600 subjects)

Randomization is stratified by the following four factors:

- Mean qualifying screening Hb ( $\leq 10.5$  vs.  $> 10.5$  g/dL)
- History of CV, cerebrovascular, or thromboembolic diseases (Yes vs. No)
- Mean prescribed weekly baseline epoetin alfa dose (or, equivalent epoetin dose for non-epoetin subjects) in the 4 weeks prior to randomization ( $\leq 150$  vs.  $> 150$  IU/kg/week)

- Geographical region (US vs. Ex-US region)

Randomization of qualified subjects will take place prior to administration of study drug.

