### 9.2 Randomization

Randomization will be stratified by the following three factors:

- Mean qualifying screening hemoglobin ( $\leq 10.5$  vs.  $> 10.5$  g/dL)
- History of CV, cerebrovascular, or thromboembolic diseases (yes vs. no)
- Mean prescribed weekly epoetin alfa dose (or, equivalent epoetin dose for nonpoetin subjects) in the 4 weeks prior to randomization ( $\leq 150$  vs.  $> 150$  IU/kg/week)
- Geographical region (US vs. Ex-US regions)

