#### 9.4.3.1 Primary Efficacy Analysis

The primary efficacy endpoint for the US (FDA) submission is defined as the Hb change from baseline to the average level during the evaluation period defined as Week 28 until Week 52. The analysis will be based on the all ITT population, Sensitivity analyses will be performed on ITT Population enrolled under the original protocol, and the ITT population enrolled under amended protocols, separately.

The primary hypothesis to be tested for the primary efficacy analysis is:

$H_0$ : Hb mean change from baseline to the average level from Week 28-to Week 52 in the roxadustat group  $\leq$  Hb mean change from baseline in the epoetin alfa group minus 0.75 g/dL

Versus:

$H_1$ : Hb change from baseline to the average level of Week 28 to Week 52 in the roxadustat group  $>$  Hb mean change from baseline in the epoetin alfa group minus 0.75 g/dL

A Multiple Imputation Analysis of Covariance (MI-ANCOVA) model will be used. The model will contain terms for baseline Hb measurement as covariate, treatment arm, and randomization stratification factors except Screening Hb values ( $\leq 10.5$  g/dL vs.  $> 10.5$  g/dL) as fixed effects. Detailed analysis of the primary endpoint will be outlined in the SAP.

In addition, as a sensitivity analysis, the primary efficacy endpoint will be analyzed using the analysis of MMRM model. The MMRM model will contain terms for baseline Hb measurement as covariate, treatment arm, visit, visit by treatment arm, and randomization stratification factors except Screening Hb values ( $\leq 10.5$  g/dL vs.  $> 10.5$  g/dL) as fixed effect. The primary efficacy analysis (for both, US [FDA] and EU regulatory submissions) will be based on the estimated difference between the two treatments overall mean effects throughout the evaluation period based on the primary analysis models.

Due to the large amount of visits to include in the MMRM model, the unstructured covariance pattern model will be tested against the less parameterized heterogeneous Toeplitz structure using the likelihood ratio test for nested models. If the algorithm for unstructured covariance pattern does not converge or the likelihood ratio test is not statistically significant then heterogeneous Toeplitz structure will be used. If this second model does not converge either then the (homogeneous) Toeplitz structure will be tried and finally compound symmetry as a covariance structure to achieve convergence.

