#### 9.4.3.2 Secondary Efficacy Analyses

Once the primary hypothesis is rejected for the primary endpoint, the secondary variables will be tested using a fixed sequence testing procedure as follows:

- For US (FDA) submission: Proportion of subjects with mean Hb level during the evaluation period defined as Week 28 until Week 52  $\geq 10.0$  g/dL.
- EU regulatory submission: Hemoglobin (Hb) response, defined as mean Hb during Weeks 28 to 36 within the range of 10.0 to 12.0 g/dL without having received rescue therapy within 6 weeks prior to and during this 8-week evaluation period.

The hypothesis to be tested for the first secondary efficacy analysis is:

H0: Hb response rate for subjects in the roxadustat group - Hb responder rate for subjects in the epoetin alfa group  $\leq -15\%$

Versus

H1: Hb response rate for subjects in the roxadustat group - Hb responder rate for subjects in the epoetin alfa group  $> -15\%$ .

A 2-sided 95% CI for the difference of two responder rates (roxadustat-ESA) based on the Miettinen and Nurminen approach adjusting for treatment group and other stratification factors will be calculated and H0 will be rejected if the lower bound of the 95% CI is greater than  $-15\%$ .

- The average monthly iron use during Weeks 1 to 36 will be compared between the 2 treatment groups using an ANCOVA model with BL iron replete as a covariate, and treatment arm and randomization stratification factors as fixed effects. Superiority will be declared if the lower bound of the 2-sided 95% CI of the difference between epoetin alfa and roxadustat exceeds 0.
- The change in low-density lipoprotein (LDL) cholesterol averaged over Weeks 12 to 28 from BL will be analyzed using an MMRM model with BL LDL cholesterol as a covariate and treatment arm, visit, interaction of treatment arm and visit, and randomization stratification factors as fixed effects. Superiority will be declared if the lower bound of the 2-sided 95% CI of the difference between epoetin alfa and roxadustat exceeds 0.
- Time to exacerbation of BP will be analyzed using the Cox Proportional Hazards model adjusting for treatment arm and randomization stratification factors. Superiority of roxadustat vs. epoetin alfa will be declared if the upper bound of the 2-sided 95% CI of the hazard ratio is  $< 1$ .

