## 9.6 Statistical Analysis Plan

The Statistical Analysis Plan (SAP) will provide details of the data analyses. As an open-label study the SAP will be finalized prior to accumulation of a substantial amount of data to ensure lack of bias. Any significant changes to the analyses described in this protocol will be highlighted in the SAP and detailed in the Clinical Study Report.

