5 GENERAL STATISTICAL CONSIDERATIONS

5.1 Sample Size Determination

At least 600 subjects and up to 1200 subjects will be randomized via IXRS to receive roxadustat or epoetin alfa in a 1:1 ratio. Study drug will be administered in an open-label manner. Randomization will be stratified by the following four factors:

- Mean qualifying screening hemoglobin (≤ 10.5 vs. >10.5 g/dL)
- History of cardiovascular, cerebrovascular or thromboembolic diseases (Yes vs. No)
- Mean prescribed baseline epoetin alfa dose (or, equivalent epoetin dose for non-epoetin subjects) in 4 weeks prior to randomization (≤ 150 vs. >150 IU/kg/week)

Up to 600 subjects will be enrolled in this study in each treatment group. During the course of this study, which is being conducted in parallel with other Phase 3 studies, up to 1200 subjects may be enrolled for safety evaluation of roxadustat in comparison to epoetin alfa including pre-specified and adjudicated safety events of interest (i.e., all-cause death, MI, stroke, congestive heart failure requiring hospitalization, unstable angina requiring hospitalization, DVT, pulmonary embolism, vascular access thrombosis, and hypertensive emergency). The final number of patients to be enrolled will be based on the enrollment rate of other studies within the same indication, in order to optimize stopping these studies at comparable time frame.

With at least 600 subjects, the study will provide at least 99% power to demonstrate statistical non-inferiority of roxadustat versus ESA in the primary endpoint for US (FDA) submission (i.e., specifically, hemoglobin change from baseline to the average level during the evaluation period defined as Week 28 until Week 52).

The study will provide at least 99% power to demonstrate statistical non-inferiority of roxadustat versus ESA in the primary endpoint outside of the United States (i.e., specifically, hemoglobin change from baseline in the averaged hemoglobin over Weeks 28 to 36). This assumes a difference (roxadustat minus ESA) of -0.30 g/dL, a non-inferiority margin for this difference of 0.75 g/dL and a standard deviation of 1.25 g/dL. Appendix 7 has description on the justification that the non-inferiority margin of 0.75 was used.

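### The SAP is inconsistent on whether geographical region, a randomization stratum, belongs in the efficacy models: section 5.4 brings it in, the list in 11.1.1.1 leaves it out without a reason

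*SAP*

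**What the plan says.** **Protocol, randomization.** The synopsis (Statistical Methods) lists four factors, one of them "Geographical region (US vs. Ex-US regions". Section 4.2 states "Randomization is stratified by the following four factors" and lists the same four. Section 9.2 states "Randomization will be stratified by the following three factors" but then lists four, region included.

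**Protocol, models.** The primary model in 9.4.3.1 contains "randomization stratification factors except Screening Hb values". Screening Hb is the only factor excepted, so region enters by reference. The same rule applies to the sensitivity MMRM, which also serves as the EU primary model. In 9.4.3.2 the secondary models use the randomization factors too; the IV iron model, for example, has a baseline iron covariate "and treatment arm and randomization stratification factors as fixed effects".

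**SAP.** Section 5.1 states "Randomization will be stratified by the following four factors" but lists three: screening Hb, cardiovascular history and ESA dose. Section 5.4 says that stratification factors derived from actual data go into all applicable models, and that the analysis factors, where suitable, are the randomization factors plus incident dialysis. Section 11.1.1.1 then says "The below stratification factors will be used in efficacy analyses" and lists screening Hb (for endpoints other than Hb), cardiovascular history, ESA dose and incident dialysis. Region is not listed and no reason is given.

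**The concern.** Two parts of the SAP give different covariate sets for the confirmatory models. A programmer who follows 5.4, reading the randomization factors as the protocol defines them, includes region. One who follows the explicit list in 11.1.1.1 does not.

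The effect spreads, because later sections refer back to the stratification factors without naming them: the EU primary MMRM (11.1.1.2), IV iron (11.2.2.4), time to transfusion (11.2.2.5), MAP (11.2.2.6) and exacerbation of hypertension (11.2.2.7).

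In an open-label trial the covariates of the primary model should be unambiguous before the data are analysed, and the analysis should normally reflect the strata used to randomize. Region could plausibly matter here. Epoetin is titrated to country-specific labels (protocol 4.5.3.2), and protocol 2.2 gives labelled Hb targets of 10 to 11 g/dL in the US and 10 to 12 g/dL elsewhere. Roxadustat aims at about 11 g/dL everywhere.

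**Working it through.** **1. Factor lists side by side**

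| Source | Screening Hb | CV history | ESA dose | Region | Incident dialysis |
|---|---|---|---|---|---|
| Protocol synopsis, 4.2, 9.2 (randomization) | yes | yes | yes | yes | no |
| Protocol 9.4.3.1 (primary model) | excepted | yes | yes | yes, by reference | no |
| SAP 5.1 (four announced, three listed) | yes | yes | yes | **no** | no |
| SAP 5.4 (analysis factors) | yes | yes | yes | yes, by reference | yes |
| SAP 11.1.1.1 (efficacy models) | non-Hb endpoints | yes | yes | **no** | yes |

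The SAP never names region as a stratum. The conflict between 5.4 and 11.1.1.1 therefore rests on the protocol's definition of the randomization factors.

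**2. The plan's own power figure**

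Inputs from SAP 5.1: true difference -0.30 g/dL, margin 0.75, SD 1.25, at least 600 subjects allocated 1:1. A two-sided 95% CI is used.

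- SE = sqrt(1.25² × 2/300) = 0.1021.
- Power = Φ(0.45/0.1021 - 1.96) = 0.9928, which agrees with the stated figure of at least 99%.

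**3. Effect of leaving region out of the linear model**

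The documents give neither the US share p nor the regional gap g. Both are assumed, as is reading 1.25 as the within-region SD. Let q = p(1 - p).

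*Only the epoetin arm differs by g.*
- Residual variance without region: 1.25² + 0.5g²q.
- With a region main effect: 1.25² + (g/2)²q. The rest is treatment-by-region interaction, which a main effect cannot remove.

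*Both arms shift by g.*
- Without region: 1.25² + g²q.
- With region: 1.25².

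Worked case, 300 per arm, p = 0.5, g = 0.5:
- Epoetin only: variances 1.5938 and 1.5781; SE 0.1031 without region and 0.1026 with; power 0.9919 and 0.9924.
- Both arms: variances 1.6250 and 1.5625; SE 0.1041 and 0.1021; power 0.9909 and 0.9928.

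Increase in SE from omitting region, p from 0.3 to 0.7:

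| Scenario | Increase in SE |
|---|---|
| Epoetin only, g = 0.25 | 0.10-0.12% |
| Epoetin only, g = 0.50 | 0.42-0.49% |
| Epoetin only, g = 0.75 | 0.92-1.09% |
| Both arms, g = 0.50 | 1.7-2.0% |

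At 600 per arm (p = 0.5, epoetin-only gap 0.5), SE is 0.0729 without region and 0.0725 with. Power is above 0.999 either way.

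**4. Bias**

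With allocation balanced within region, both arms have the same regional mix, so with complete data the linear treatment difference has the same expectation with or without region. Simulation (4,000 trials per setting, 300 per arm, epoetin-only gap 0.5, assumed baseline Hb covariate with SD 0.7 and slope -0.5, no missing data) agreed. SE was about 0.103 without region and 0.1025 with, and the mean estimate was -0.30 to within simulation error under both models.

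**The case against.** The strongest reply is that region has not been dropped at all. SAP 5.4 requires the stratification factors in all applicable models, the SAP presents itself as an elaboration of protocol Amendment 2, no sentence removes region, and the list in 11.1.1.1 does not claim to be exclusive. With four factors announced and three listed in 5.1, a lost bullet is at least as plausible as a changed model. This stands: the defect is an inconsistency within the SAP, and the documents do not show whether it is a slip or a decision. It does not remove the point, because an analyst still has two texts to choose between.

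A reader might infer a breach of protocol 9.6, which says "Any significant changes to the analyses described in this protocol will be highlighted in the SAP". The documents do not support that. The duty covers significant changes only, the numerical effect is small, SAP 5.4 still calls for the randomization factors, and protocol 9.4.3.1 leaves detail of the primary analysis to the SAP.

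A reader might also infer that the non-inferiority conclusion is at risk. In the scenarios computed it is not: the SE without region is slightly too large, which works against declaring non-inferiority. The opposite inference, that omission is harmless in every model, is not supported either. In a Cox model, leaving out a prognostic factor can change the hazard ratio even under balance. The imputation step in 11.1.1.1 uses a baseline stratification factor that it does not identify; if region predicts both dropout and Hb, balance at randomization does not settle the matter.

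Finally, the losses of power shown depend on taking 1.25 as the within-region SD. If it is the overall SD, power without region is simply the planned 0.9928, and including region would raise it slightly.

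**Conclusion.** The point holds as an internal inconsistency in the SAP: 5.4, read with the protocol's list of strata, includes region, while 5.1 and 11.1.1.1 omit it and give no reason. Taken literally, 11.1.1.1 would leave a randomization stratum out of both primary models and the dependent secondary models.

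For the linear primary model with complete data the consequence is small: no bias, an SE inflated by at most about 2% in the scenarios examined, and power above 99% at 300 per arm. This is conditional on the assumed regional gaps, a US share of 30-70% and a within-region SD of 1.25 g/dL. Effects on the Cox and proportion analyses, and through the imputation, were not assessed. The reason to act is clear pre-specification at almost no cost, not a threat to the result.

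**What to change.** - Add region (US versus Ex-US) to the factor lists in SAP 5.1 and 11.1.1.1, and keep incident dialysis in 11.1.1.1. The list then agrees with SAP 5.4 and contains every factor that protocol 9.4.3.1 requires.
- State in the SAP that incident dialysis is an addition to the protocol 9.4.3.1 model, which has no such term. Its basis is the stratification of the US analyses by amendment in protocol 9.3.
- If region was left out on purpose, say so in the SAP, give the reason, and align 5.4.
- Separately, correct the count in protocol 9.2 from three to four. This is a clerical slip.

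The cost is wording plus one model degree of freedom. Region is already a randomization factor and is already in the baseline summaries (SAP 7), so no new data are needed.

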## 4 STUDY DESIGN

### 4.1 Description of the Study

This open-label, randomized, active controlled study is designed to evaluate the efficacy and safety of roxadustat compared to epoetin alfa for the maintenance of hemoglobin (Hb) levels in subjects on HD or PD or HHD originally on ESA for treatment of anemia.

- **Screening Period:** Up to 6 weeks. For subjects currently taking Mircer®, the Screening Period can be extended up to 8 weeks
- **Treatment Period:** Treatment duration is variable for individual subjects, with a minimum treatment duration of 52 weeks and a maximum duration of up to approximately 3 years after the last subject is randomized

**Amendment 1& 2:** In order to complete the Phase 3 program in a timely manner, minimum treatment duration of subjects enrolled under Amendment 1 & 2 may be shortened. Subjects will be informed at least 4 weeks in advance if such decision is made. All active subjects will end the study at the same time

- **Post-Treatment Follow-Up Period:** 4 weeks

During the course of the study, visits and assessments will be performed as defined in the schedule of assessments.

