11.1.3 Subgroup Analyses

The analysis of the primary endpoints of US and Ex-US may be performed by gender, age group, baseline hemoglobin categories, mean prescribed weekly epoetin alfa dose categories, baseline CRP categories, cardiovascular/cerebrovascular/thromboembolic medical history, baseline iron replete status, and stable vs incident dialysis: dialysis duration >4 months vs ≤ 4 months where appropriate.

In addition, hemoglobin change from baseline to the average level during Weeks 18-24 may be analyzed by subgroups of baseline hs-CRP (\leq ULN, vs. $>$ ULN), baseline ESA dose categories, and dialysis status.

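### SAP 11.1.1.1 does not clearly keep incident-dialysis status and the other ANCOVA factors in the primary imputation model after Week 1

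*SAP*

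**What the plan says.** SAP 11.1.1.1 (U.S. Submission) defines the primary analysis model: "The model will contain terms for treatment group, baseline Hb measurement, and stratification factors except mean qualifying screening hemoglobin". The list of efficacy factors in the same section names cardiovascular history, prior ESA dose category, and dialysis for at most versus more than 4 months at randomization.

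The imputation is described in two steps.

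- Step 1 fills intermittent gaps by MCMC, "relying on non-missing data from all subjects within each treatment group". Only Hb at scheduled weeks is listed.
- Step 2 fills the missing ends. For the first visit: "Missing data at Week 1 will be imputed using the regression imputation model with baseline stratification factor, baseline and hemoglobin from Week 1". The factor is singular and unnamed, and Week 1 Hb appears among the predictors of Week 1 Hb.
- Step 2 then works by arm: "The SAS PROC MI procedure will use data separately from each treatment subjects to impute the missing data for a specific Week". It goes on: "Repeat for all other scheduled Weeks sequentially (Week 2 to the end of evaluation period".
- The last line of step 2 is: "The regression imputation model includes an intercept and the slopes of the hemoglobin from previous Weeks".

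Protocol 4.1 says that "minimum treatment duration of subjects enrolled under Amendment 1 & 2 may be shortened", and that all active subjects will finish together. The Protocol synopsis plans about 150 incident subjects under Amendments 1 and 2. SAP 11.1.3 allows the primary endpoint to be analysed by several subgroups, including "baseline iron replete status, and stable vs incident dialysis".

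**The concern.** An imputation model should contain at least the variables of the analysis model, above all one linked to the chance of being missing. Incident status may be such a variable here. The amendment cohort consists of incident subjects, and it is the cohort whose treatment may be cut short before the Weeks 28 to 52 evaluation period is complete.

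If the weekly regressions contain only earlier Hb, a truncated incident subject's later values are predicted from a same-arm regression fitted mostly to stable subjects. Whatever part of the incident course is not already visible in that subject's own earlier Hb is lost. At stake are the incident coefficient, any stable-versus-incident result that reuses the pooled imputations, and, in narrower circumstances, the overall treatment difference. The text also fails to fix one primary model: two programmers could follow it faithfully and fit different regressions.

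**Working it through.** **Inputs from the documents.** Margin 0.75 g/dL, planning difference -0.30 g/dL, SD 1.25 g/dL, 600 to 1200 subjects allocated 1:1, two-sided 95% CI (SAP 5.1 and 11.1.1.1). About 150 incident subjects (Protocol synopsis): 150/1200 = 12.5%, 150/600 = 25%.

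**The plan's own figure first.** The distance to the margin is 0.75 - 0.30 = 0.45 g/dL. With 300 per arm, SE = 1.25 × √(2/300) = 0.102. Power = Φ(0.45/0.102 - 1.96) = Φ(2.45) = 0.993, so the stated figure of at least 99% reproduces.

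**Simulation of the literal reading.** The documents do not give the share or timing of truncation, or the incident Hb course, so these are assumptions:

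- 60,000 subjects per arm, 4-weekly visits, per-visit SD 1.0, compound-symmetric plus AR(1) correlation.
- Incident share 12.5%, 20% or 25%.
- 50% or 90% of incident subjects, and 15% of stable subjects, last observed at Week 24, at the same rates in both arms.
- Sequential regression imputation within arm, with and without an incident term. The ANCOVA then uses treatment, incident status and baseline.
- Bias is the estimate after imputation minus the complete-data estimate.

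**Incident coefficient (g/dL), with the same 0.5 g/dL deviation in both arms:**

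| Deviation | Complete data | Factor omitted, 50% truncated | Factor omitted, 90% truncated |
|---|---|---|---|
| Grows from Week 20 | about 0.31 | about 0.19 | about 0.06 |
| Present from the first visit | about 0.50 | 0.44 to 0.46 | 0.39 to 0.40 |

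In these rows the bias in the treatment difference is at most 0.003 g/dL.

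**Bias in the treatment difference (g/dL), factor omitted, when the late deviation differs by arm.** Each cell runs over incident shares of 12.5%, 20% and 25%:

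| Deviation at Week 52, roxadustat / epoetin | 50% truncated | 90% truncated |
|---|---|---|
| +0.5 / 0 | -0.014, -0.017, -0.026 | -0.030, -0.048, -0.063 |
| +1.0 / 0 | -0.028, -0.040, -0.045 | -0.061, -0.095, -0.119 |
| -0.5 / +0.5 | +0.025, +0.036, +0.047 | +0.059, +0.098, +0.118 |

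With the incident term in every step, bias is at most about 0.01 g/dL in all 30 scenarios.

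**A separate, smaller simulation of the subgroup result.** It used 1,200 subjects, 12.5% incident, incident follow-up ending uniformly over Weeks 12 to 52, 25% other dropout, and incident drift building over Weeks 20 to 36. A true incident-subgroup difference of -0.45 g/dL was estimated as -0.18 with the factor omitted and -0.44 with it included. The overall difference of -0.056 became -0.022 and -0.051 respectively. Without incident-specific drift there was no material bias.

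**Consequence for the test, 300 per arm, bias against roxadustat:**

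- 0.05: Φ(0.40/0.102 - 1.96) = 0.975.
- 0.10: Φ(0.35/0.102 - 1.96) = 0.929.
- 0.119 (worst case, 25% incident): Φ(0.331/0.102 - 1.96) = 0.90.

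With 600 per arm, SE = 1.25 × √(2/600) = 0.072. The worst bias at 12.5% incident is 0.061, giving Φ(0.389/0.072 - 1.96), which exceeds 0.999.

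**The case against.** The strongest reply is that the SAP may already do what is asked. The Week 1 regression has a stratification term, later weeks repeat the procedure, and the closing line does not say that its list is exhaustive. That stands: the text is ambiguous, and a reader who infers that the factors are definitely dropped goes beyond it. The ambiguity is still worth removing, because even the Week 1 text does not name incident dialysis and step 1 names no factor at all.

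A reader might also infer that incident subjects' missing values are simply copied from stable subjects. The documents do not support this. Donors are all same-arm subjects, including incident ones with later data, and each value is conditioned on the subject's own earlier Hb. Hb is scheduled at 13 visits from Week 1 to Week 24, and the simulation shows that a deviation already visible there is mostly retained.

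Nor do the documents say that incident follow-up will be truncated. Shortening is an option, with no share or timing given. The incident factor and the amendment cohort are also not identical. The original protocol required at least 3 months of dialysis before screening, so some of its subjects could be randomized within 4 months, and the shortening option does not cover them.

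Other planned analyses give partial cover. Protocol 9.4.3.1 asks for separate analyses of the original-protocol and amended-protocol ITT cohorts, and running the imputation within the amended cohort would avoid borrowing from original-protocol subjects. SAP Table 5 lists the original-protocol MI-ANCOVA, which cannot show bias inside the cohort it leaves out. The MMRM sensitivity analysis carries the factors, but as main effects without an incident-by-visit or incident-by-treatment term. The stable-versus-incident subgroup analysis is optional, and the SAP does not say whether it would reuse the pooled imputations. If it imputed within subgroup, that distortion would not arise.

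**Conclusion.** The point holds as a specification gap with limited consequences. On the literal reading, the imputation model is narrower than the ANCOVA for a factor tied to follow-up that may be shortened. The effect falls mainly on the incident coefficient and on any stable-versus-incident result drawn from the pooled imputations.

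A reader might infer that the gap biases the primary comparison in favour of non-inferiority. That is not supported. The overall difference is affected only if the incident deviation or the truncation differs by arm. An arm-specific deviation gave about 0.01 to 0.12 g/dL. Arm-specific truncation was not simulated. The direction depends on which arm does worse in incident subjects. Against 0.45 g/dL of headroom, a changed conclusion is unlikely under the planning assumptions. That statement rests on the planned difference of -0.30 and SD of 1.25, and the bias range rests on assumed truncation and assumed late Hb courses. It would be less comfortable if the true difference lay close to the margin.

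**What to change.** In SAP 11.1.1.1, state that baseline Hb, every factor in the ANCOVA (named, including incident dialysis) and all earlier Hb values enter both the MCMC step and each weekly monotone regression, within arm. Remove Week 1 Hb from the predictors of Week 1.

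Add a fallback for any week at which an arm has too few observed incident subjects to estimate the incident term. Without it the fix fails exactly where truncation is heaviest, because the term cannot be estimated if nobody in that stratum is observed. Also say whether subgroup analyses reuse the pooled imputations or impute within subgroup.

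The cost is a sentence or two and a few variables in PROC MI, with no new data. The downside is a few more parameters per weekly regression.
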